 - drug group x session interaction ($p<0.05$) followed by MEM+TCT > PBO+TCT at specific session # or combination;
4. **More durable** clinical, neurocognitive **or** functional gains:
 - MEM+TCT > PBO+TCT at post-TCT week 12.

PANSSt: *Positive & Negative Symptom Scale total*; MCCB-C: *MATRICS Composite*; Fnxn: *Function (assessed via the World Health Organization Disability Schedule 2.0 (WHODAS))*

Rhythm Recall: Subjects listen to and replicate a short rhythmic sequence. This task is designed to stimulate both basic auditory processes supported by primary auditory cortex, and non-verbal auditory WM.

Symptoms are assessed to track clinical status and TCT response. TCT reduces positive symptoms of psychosis, and we predict that MEM will augment these effects via enhanced TCT learning (i.e. not via a lasting direct pharmacological effect of MEM), detected by the Positive & Negative Syndrome Scale. For this reason, and based on the need to limit total outcome measures, **PANSS Total Score is the primary clinical outcome measure**. Positive and negative symptom subscales, as well as PANSS factor-derived measures, will be assessed in exploratory analyses. Other secondary clinical measures will include: 1) Psychotic Symptom Rating Scales (PSRS; assesses auditory hallucinations); 2) Young Mania Rating Scale; 3) Patient Health Questionnaire-9 (PHQ-9; current depressive symptoms); 4) Abnormal Involuntary Movement Scale (AIMS); 5) **C-SSRS**; “Lifetime/Recent version” at screen; “Since Last Visit” at follow-up visits). The C-SSRS is a reliable, valid and sensitive measure of suicidal ideation⁹⁸; *any “yes” in C-SSRS prompts an immediate full evaluation/action plan by a study M.D.; and* 7) MEM Cessation Symptom Assessment (ACSA).

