Post-treatment protocol: On completion of 30 TCT sessions, participants will be offered the option of maintaining their assigned drug (PBO or MEM) through the 22-week durability assessments. Those who opt to discontinue the study drug will titrate off, over a 3-week period. After week 22, study blind will be broken, and subjects who continued to receive MEM will again be offered the option of titrating off of MEM vs. maintaining MEM treatment coordinated with, and under the supervision of, their primary provider.

Data Analysis: “Go/No Go” decisions are based on traditional statistical significance (Aim 1) and effect sizes (Aim 2). Formal statistical testing is conducted using linear mixed-effects (LME) models; hypothesis tests are 2-sided ($\alpha=.05$). Model parameters are estimated via the R lme4 package and Cohen’s d is estimated via the

EMAtools package. Type I errors are minimized by constraining the number of primary analyses; secondary analyses use false discovery rate corrections. Expected attrition rates are described above. Because outcome measures involve a “change from baseline”, baseline metrics are compared between PBO and MEM arms, and any baseline differences are addressed in the outcome analyses. Differential drop-out rates from PBO vs. MEM arms are monitored. Data are assumed to be missing at random; full information maximum likelihood estimators are used, and all data/cases are included in analyses. Clinical follow-up is pursued with all patients exiting the study through post-TCT week 12. Cohort differences: For between-subject contrasts (main effect of drug), differences in age, antipsychotic and anticholinergic loads are tested and used as covariates^{2,33,95}. Sex differences are tested for all measures. NIH Data Harmonization: 3 “PhenX Toolkit” (NOT-MH-15-009) measures of function are used; see above and “Resource Sharing Plan”.

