Aim 1 – Confirm target engagement: The primary dependent measure of target engagement is MEM-enhanced APS learning. APS learning is defined as the reduction in Sound Sweeps APS threshold (ms) Test 1 to Test 2 assessment. Target engagement was demonstrated in Fig. 3⁷⁶, and will be confirmed if APS learning is increased by MEM (note that MEM and PBO groups are matched by Test 1 PBO performance via stratified randomized assignment). As appropriate, effect sizes and inferential statistics are based on standard regression or LME models with random intercepts. A significant interaction between contrast coded drug (PBO vs. MEM) and Test (Test 1 vs. Test 2) predictors on APS learning is a “Go” criteria and confirms target engagement.

Aim 2 – Test clinical, neurocognitive and functional impact of MEM on TCT, and its relationship to target engagement: We will determine if MEM+TCT produces greater, faster or more durable clinical, neurocognitive or functional gains from baseline, compared to PBO+TCT, over a 30-session course of TCT. A Cohen’s $d > 0.5$ for the main effect of drug (PBO vs. MEM) or drug x session (#10, 20, 30) interaction in an LME model is the primary “Go” criteria. The effect of drug assesses “greater” gains. Reverse Helmert contrasts for session assesses “faster” gains. A separate model comparing differences in outcomes at 12-weeks post-TCT assesses “more durable” gains. Secondary analyses will examine whether change in MEM-enhanced APS learning (“within-subject” target engagement; Aim 1) predicts gains in Aim 2 outcome measures.

Aim 3 – Biomarkers of MEM-induced gains: We will determine if baseline levels of specific neurocognitive or EEG-based measures, or changes in specific measures with initial MEM exposure (Test 2 vs. 1), predict greater sensitivity to MEM-enhanced neurocognitive, clinical or functional gains over 30-h of TCT. Regression analyses will assess whether specific candidate biomarkers predict MEM-enhanced gains in outcome measures.

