"Go/No-Go" decisions are based on traditional statistical significance (Aim 1) and effect sizes (Aim 2). Formal statistical testing is conducted using linear mixed-effects (LME) models; hypothesis tests are 2-sided ($\alpha=0.05$). Model parameters are estimated via the R lme4 package and Cohen's d is estimated via the EMAtools package. Type I errors are minimized by constraining the number of primary analyses; secondary analyses use false discovery rate corrections.

PANSSt scores will be assessed at specific intervals. Because TCT is associated with improvements in both positive and negative symptoms, our *a priori* hypothesis is that a PACT effect will be evident in both positive and negative symptoms. Hence, PANSSt is used as the primary metric of symptomatic gains. A greater reduction in PANSSt score will be detected using data from baseline through TCT 30h, by a significant main effect of group (arm) or a significant interaction of group x session, with post-hoc contrasts revealing significant group differences at TCT 30h. A faster reduction in PANSSt scores will be detected using these same data by a significant interaction of group x session and a significant group difference at a point prior to TCT 30h. A more durable reduction in PANSSt scores will be detected using data from TCT 30h through 12 weeks post-TCT, by a significant main effect of arm or a significant interaction of group x post-TCT day, with post-hoc contrasts revealing significant group differences 12 weeks post-TCT.

Comparable analytic approaches will be used for neurocognition (MCCBc) and function (WHODAS) as described in "Research Strategy". Data will be described as means with SEM. Tests for normalcy will be applied to all data and non-parametric comparisons will be used if normalcy is not demonstrated. The Analysis Set for these data will be all subjects who have completed 30h of TCT and post-TCT clinical, neurocognitive and function assessments. When appropriate, missing data are handled via multiple imputation or full information maximum likelihood estimation.

Secondary regression analyses assess the predictive value of putative biomarkers on clinical, neurocognitive or functional gains from the addition of MEM to TCT. Future studies with larger samples will assess potentially more informative models, e.g. Path Analysis to study moderating effects of APS MEM sensitivity and biomarkers on both indirect (moderated-mediation) and direct paths between treatment and outcome.

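### As written, the durability Go criterion is modelled without the session 10 and 20 scores, so the plan's missing-at-random protection does not reach patients lost during training

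*Combined protocol and SAP*

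**What the plan says.** Three parts of the combined document bear on this.

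**The criterion.** Table 1 (Research Strategy) lists durability as Go criterion 4: "MEM+TCT > PBO+TCT at post-TCT week 12", with d above 0.5. Criterion 1 plus any one of criteria 2 to 4 is enough, subject to the separate condition on adverse effects.

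**The model.** In the Aim 2 paragraph of Data Analysis, the sentence on durability begins "A separate model comparing differences in outcomes at 12-weeks post-TCT assesses". Section 4.4, under the Go/No-Go heading, gives the data window for the PANSS total: "A more durable reduction in PANSSt scores will be detected using data from TCT 30h through 12 weeks post-TCT". It extends a comparable approach to the MCCB composite and WHODAS. All three outcomes are also collected at baseline and after sessions 10 and 20, but neither description brings the session 10 and 20 scores into the durability model.

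**The missing-data position.** Data Analysis assumes data are missing at random and states that "full information maximum likelihood estimators are used, and all data/cases are included in analyses". Section 4.4 says otherwise: "The Analysis Set for these data will be all subjects who have completed 30h of TCT and post-TCT clinical, neurocognitive and function assessments". The plan also pursues clinical follow-up of patients who exit, through post-TCT week 12. Section 4.4 allows multiple imputation or full-information likelihood when appropriate, and says auxiliary variables will be explored. None of these is tied to the durability model.

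**The concern.** Maximum likelihood under missing at random can condition only on data inside the model being fitted. A patient who leaves after session 10 or 20, and has neither a 30-hour nor a week-12 score, adds no row to a model that starts at 30 hours. The scores most likely to explain the departure are then unused, and the week-12 contrast compares those who stayed. Relabelling the population as all randomised patients does not change this, because the gap lies in which visits enter the model.

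At stake is a route that can carry the Aim 2 Go without the other two. If patients doing badly leave the memantine arm while placebo losses are unrelated to response, the retained memantine patients look better at week 12 than the whole arm would have.

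**Working it through.** **1. How many patients are exposed.** The plan gives no sample size or power for durability. Its planning figures are in the subject throughput paragraph: 12 TCT completers a year over 3 years = 36, or 18 per arm, against 27 per arm tested for target engagement. Loss during training = (54 − 36)/54 = 33.3%. The plan calls this conservative.

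**2. What each model can use.**

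| Patient | Separate model (30 h to week 12) | All-visit model |
|---|---|---|
| Leaves between 30 h and week 12 | 30-hour score | all scores to 30 h |
| Leaves after session 20 | nothing | baseline, sessions 10 and 20 |
| Leaves after session 10 | nothing | baseline, session 10 |

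The gap therefore concerns loss during training. Loss after 30 hours is covered in the section 4.4 version.

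**3. Size, true difference 0.30.** Assumptions, none given by the documents for these outcomes:
- 27 per arm, five visits, within-patient correlation 0.7.
- True difference of 0.30 SD in change at session 30 and week 12.
- Drop-out logit before each of sessions 10, 20 and 30 of −2.0, minus slope × last observed gain where drop-out depends on response.

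With slope 0 the logit gives 1/(1 + e²) = 0.119 per interval, so 0.881³ = 68% complete, close to the plan's 18/27 = 67%. Odds ratios per SD of gain are e^0.5 = 1.6, e^1.0 = 2.7 and e^2.5 = 12. The separate model is the week-12 change contrast in retained patients. The all-visit model is a multivariate-normal likelihood fit. Ranges come from repeated sets of runs.

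| Drop-out depends on gain in | Odds ratio | Separate, mean | All-visit, mean | P(estimate > 0.5), separate vs all-visit |
|---|---|---|---|---|
| MEM only | 12 | 0.45–0.46 | 0.29–0.31 | 42% vs 21–24% |
| MEM only | 2.7 | 0.36–0.39 | 0.29–0.33 | 28% vs 18% |
| MEM only | 1.6 | 0.34 | 0.31 | 26% vs 22% |
| both arms alike | 2.7 | 0.28 | 0.29 | 18% vs 17% |
| neither | 1 | 0.31 | 0.32 | not tabulated |

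The estimator's SD is about 0.25, so with 300 to 400 runs the simulation error of a mean is about 0.25/√300 = 0.014 to 0.25/√400 = 0.013. Gaps of 0.01 are noise; gaps of 0.06 or more are not. With a true difference of 0 and an odds ratio of 2.7 in MEM only, the bias is about 0.09, and the chance of exceeding 0.5 is 7% against 2%.

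**4. A second set of assumptions.** Here 2,500 runs per scenario were used, about a third of patients were lost, and drop-out was either random or depended on the session 20 change at two strengths. Correlations were 0.6 or 0.8 (equal), or 0.8 decaying with time.
- Random drop-out: no bias.
- Same mechanism in both arms: no bias at a true difference of 0; a true 0.5 averages 0.42 to 0.47.
- MEM only, true 0: change from baseline in retained patients averages 0.09 to 0.30 and exceeds 0.5 in 2% to 30% of trials, against 1% to 8% for the all-visit model. Adjusting for baseline alone leaves 0.07 to 0.20. If raw week-12 scores were compared instead of change, the mean is −0.01 to 0.12.
- Opposite mechanisms by arm (extreme), true 0: 0.18 to 0.59.
- All-visit model, every scenario: −0.01 to 0.02 at true 0, and 0.49 to 0.51 at true 0.5.

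**The case against.** A reader might infer that patients who withdraw are necessarily excluded from the durability analysis and that their earlier scores cannot be used. The documents do not support that. Exiting patients are pursued to post-TCT week 12, so some could supply week-12 scores. Multiple imputation is permitted, and imputing from all visits would bring sessions 10 and 20 in. Section 4.4 itself raises outcome-related drop-out and proposes auxiliary variables, for which earlier scores would qualify. The Aim 2 paragraph does not list the visits in its separate model, so reading it as week 12 alone is also an inference.

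What stands is that these are possibilities and not commitments. The follow-up is described as clinical, without naming the PANSS, MCCB or WHODAS. Imputation is conditional and no auxiliary variables are named. The completer set in section 4.4 would exclude withdrawn patients anyway.

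A reader might also infer that the durability result will be biased towards Go. That does not follow either. Nothing in the documents indicates that drop-out will depend on response, or differently by arm. The largest figures need an odds ratio of about 12 per SD in one arm only. At moderate dependence the bias (0.03 to 0.07) is well below the estimator's SD of about 0.25. Monitoring drop-out rates by arm, which the plan does, is some safeguard, but equal rates can hide different reasons.

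Finally, the completer set is the most direct source of exclusion. Correcting it alone, however, would leave the data window unchanged.

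**Conclusion.** The point holds as a gap in specification. As written, session 10 and 20 scores are not used in the durability model, so the protection claimed in Data Analysis does not extend to the up to one third of patients who may leave during training, unless one of the uncommitted remedies is applied.

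The consequence is conditional. There is none if drop-out is random. If the same mechanism acts in both arms, the two models agree closely at a true 0.30, and a true 0.5 is somewhat understated. Under moderate MEM-only dependence a true 0.30 is read as about 0.34 to 0.39, and near the worst case as about 0.45, against 0.29 to 0.33 from an all-visit model. These sizes rest on assumed correlations and drop-out mechanisms, on analysing change from baseline, and on SD units standing in for the plan's Cohen's d. The all-visit model corrects only under missing at random, which the plan already assumes.

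The change should be made because the criterion can by itself satisfy the Aim 2 efficacy requirement and the remedy needs no new data. Confidence in the size is moderate at best.

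**What to change.** In the Aim 2 paragraph and in section 4.4, replace the separate durability model with one longitudinal mixed model per outcome in all randomised patients. Include baseline, sessions 10, 20 and 30 and post-TCT week 12, with visit as a factor and arm by visit. Read criterion 4 as the arm contrast in change from baseline at week 12. Alternatively, keep a separate week-12 analysis but prespecify multiple imputation from all visits. In either case, reconcile the completer analysis set in section 4.4 with the statement in Data Analysis that "all data/cases are included in analyses", and say whether the outcome scales are collected at week 12 in patients who withdrew.

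Cost: a change of wording, no new data, and almost no loss of precision (SD about 0.26 against 0.25 for the separate model). There are two drawbacks. An unstructured covariance over five visits has 5 × 6/2 = 15 parameters, to be estimated from 54 patients, some without later visits. And lme4, the package the plan names, does not fit residual covariance structures, so anything richer than a random intercept needs other software such as nlme or mmrm. The richer structure is preferable: with correlations that decay over time and severe MEM-only drop-out, a random-intercept fit still averaged 0.38 for a true 0.30. The plan should name the covariance structure and a simpler fallback in case the model does not converge.

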Outcome and “Go Decisions”. In addition to confirming “target engagement”, this application tests the hypothesis that SZ patients given MEM +TCT will exhibit greater, faster and/or more durable improvements (change from baseline) in symptoms, neurocognition and/or function compared to patients given PBO+TCT, and that this enhanced clinical response will be associated with greater MEM-enhanced TCT learning.

The small “n” necessitated by the 3-year timeline and demanding treatment schedule greatly constrains the total number of outcome measures.

Moreover, the plan to assess not only magnitude but also rate and durability of PACT gains triples the number of primary analyses. Thus, we selected only one **primary** clinical, neurocognitive and functional outcome measure (Table 1) – recognizing that they are relatively “blunt” metrics - but will track several other, more focused, measures as well as inter-measure correlations in exploratory analyses to inform future studies.

A “Go” decision requires: 1) confirmation of target engagement (APS learning, MEM>PBO, p<0.05); 2) evidence of gains from PACT ($d \geq 0.5$ (MEM > PBO)) in primary clinical, neurocognitive and/or functional measures (Table 1), and 3) the absence of adverse effects of MEM that are significantly greater than PBO levels. The decision to not use traditional statistical significance as “Go” criteria for Aim 2 reflects this RFA’s call for “Pilot” studies, the need to identify candidate treatments for a subsequent larger “n” Confirmatory Efficacy R01 study, and the limits in sample size resulting from the 3-year R33 duration. Cohen defined a medium effect size ($d=0.5$) as one that is “visible to the naked eye,” and this amount of change is viewed as clinically meaningful in trials targeting negative symptoms.⁹⁹⁻¹⁰¹ This $d=0.5$ “Go” threshold for Aim 2 corresponds to a “number needed to treat” (NNT) value ≈ 3.62 . While a “Go” decision does not require identification of a biomarker predicting greater PACT sensitivity (Aim 3), the identification of one or more meaningful predictors that could be incorporated into a Confirmatory Efficacy trial would favorably impact a “Go” decision.

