Staff assessing outcome measures are blind to treatment arm, and for some measures receive training using videotaped and practice interviews until achieving high (ICC>.80) reliability based on 20 assessments by 2 raters. We achieve high inter-rater reliability (e.g., ICC>0.85 for PANSS total), and check for rater drift each 90d.

Specific Procedures: TCT is completed with a dedicated room and equipment. Staff trained with a UCSD-developed “TCT Clinician Competence Assessment” monitor TCT, clarify instructions and provide encouragement as needed. **In the initial “biomarker testing” session (Test 1),** subjects complete 1-h of Sound Sweeps to generate a “Pre-Training APS score” as described previously (Fig. 3) under identical circumstances and timelines as for the Test 2 session described below. Treatment group assignment (PBO vs. MEM) is then made using stratified random sampling (above) and 5-7 days later patients ingest either PBO (n=27) or 20 mg MEM (n=27) 240 min before completing the Sound Sweeps session (“Test 2”). MEM effects on APS learning are assessed both within-subject (APS (Test 1 - Test 2) for MEM group subjects: a key measure of **MEM sensitivity**) and between subjects (APS Test 2, PBO vs. MEM groups). After Test 2, all subjects are prescribed daily PBO or MEM using a standard titration schedule (MEM 5 mg at hs→ 5 mg bid→ 5 mg am/10 mg hs→ 10 mg bid over 3 weeks). Participants return to the laboratory to complete 1h TCT per our established procedures^{2,34}, which includes 5 modules of auditory/verbal processing exercises. Each module increases in difficulty as performance improves: **1) Sound Sweeps; 2) Syllable Identification:** Patients distinguish between 2 similar phonemes (e.g., “ba” vs. “da”), differing only in their voice onset time; **3) Word Matching:** Subjects match short similar-sounding consonant-vowel-consonant words (e.g., bad, dad); **4) Listen & Do:** Subjects reconstruct a spoken series of instructions and use a computer mouse to click icons on the screen in a specified order. This exercise is designed to stimulate verbal WM processes supported by the lateral PFC as well as premotor and motor processes. **5)**

Table 1. “Go” criteria: #1, plus at least one of #'s 2, 3 & 4 ($d>0.5$)

1. **Target engagement:** APS learning, MEM > PBO, p<0.05
2. **Greater** clinical, neurocognitive **or** functional gains:
 - ↓PANSSt, ↑MCCB-C **or** ↑Fnxn: MEM+TCT > PBO+TCT
3. **Faster** clinical, neurocognitive **or** functional gains:

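### The criterion for 'more durable' gains tests benefit present at week 12, not retention; the one retention term, in Section 4.4, is optional and has no direction

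*Combined protocol and SAP*

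**What the plan says.** The rule appears in three places, in three forms.

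- Research Strategy, Data Analysis, Aim 2: "A separate model comparing differences in outcomes at 12-weeks post-TCT assesses" more durable gains. The same paragraph frames the question as "more durable clinical, neurocognitive or functional gains from baseline, compared to PBO+TCT", so the reference point is baseline, not session 30.
- Table 1, item 4: "MEM+TCT > PBO+TCT at post-TCT week 12". Go needs item 1 plus any one of items 2 to 4, with d above 0.5.
- Section 4.4, Go/No-Go decision and primary and secondary endpoints (written for PANSS total, with comparable approaches for the MCCB composite and WHODAS): the analysis is done "using data from TCT 30h through 12 weeks post-TCT", and durability is shown by "a significant main effect of arm or a significant interaction of group x post-TCT day, with post-hoc contrasts revealing significant group differences" at 12 weeks.

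The plan treats durability as its own question. The Research Strategy paragraph on outcomes and Go decisions says that "the plan to assess not only magnitude but also rate and durability of PACT gains triples the number of primary analyses", and point 10 of the question-and-answer list speaks of memantine prolonging gains from training.

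**The concern.** Saying that gains are more durable means that more of what was there at the end of training is kept. A comparison of arms at week 12 does not measure that. It shows whether memantine is ahead at follow-up, which may simply be the remainder of a larger lead at session 30.

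The Section 4.4 version does not close the gap. An arm main effect over session 30 and week 12 averages the two visits and says nothing about change between them. The interaction does concern change, but the sentence accepts either term and sets no sign for the interaction.

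At stake is one of the three claims the pilot hands to a confirmatory trial: that adding memantine makes training gains last better. As written, that claim could be made when the data show the advantage fading.

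**Working it through.** **The plan's own figure.** No power or error rate is given for durability. The only sample-size figure is 27 per arm for Aim 1 (d = 0.5, 80% power, two-sided 0.05, test-retest correlation 0.8). It reproduces: the SD of change is √(2 × (1 − 0.8)) = 0.632, and power by the noncentral t is 79.8% at 26 per arm and 81.3% at 27. The point below does not depend on it.

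**Identity.** Write D30 and D12 for the arm differences (memantine minus placebo, positive = improvement) at session 30 and week 12, and R for the arm difference in change between them. Then

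D12 = D30 + R.

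Table 1 item 4 looks at D12 only. With D30 = 1.0 and R = −0.4, D12 = 0.6, and the item is met on the true values although 0.4 SD of the advantage has gone.

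**How often the rule is met.** Inputs: 27 per arm (randomised) and 18 per arm (expected completers), from the Research Strategy. Assumptions, because the documents give none: SD 1 at each visit, between-visit correlation 0.5 or 0.8, and the mean gains below. With a true D12 of 0.6, the noncentral t gives P(observed d > 0.5) = 0.620 at 18 per arm and 0.644 at 27. D30 does not enter. Simulation of both visits (20,000 trials per cell) gives:

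| Assumed gains, session 30 → week 12 (SD) | D30 → D12 | Item 4 met | Retention contrast significant for memantine |
|---|---|---|---|
| A: placebo 0.4 → 0.4, memantine 1.2 → 1.0 | 0.8 → 0.6 | 62–65% | at most 0.5% |
| B: placebo 0.4 → 0.3, memantine 1.4 → 0.9 | 1.0 → 0.6 | 62–65% | at most 0.2% |
| C: placebo 0.4 → 0.4, memantine 1.0 → 1.0 | 0.6 → 0.6 | 62–65% | 2–3% |
| D: placebo 0.8 → 0.2, memantine 0.8 → 0.8 | 0.0 → 0.6 | 62–65% | 42–79% (n = 18), 59–93% (n = 27) |

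In B memantine fades faster on either scale: it loses 0.5 SD against 0.1, and keeps 0.9/1.4 = 64% of its gain against 0.3/0.4 = 75%. Item 4 does not tell A, B, C and D apart; the retention contrast does.

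**Section 4.4 in scenario B.**

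- Either term plus a significant week-12 difference: about 42% of trials at 18 per arm, 58% at 27.
- Arm main effect alone, if the post-hoc condition is read as applying only to the interaction: about 70–77% and 86–91%.
- Significant interaction in the wrong direction plus a significant week-12 difference: 4–14% and 11–32%. These trials would qualify through the retention term itself.

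**Precision of the retention contrast.** SE = √(2(1 − ρ)) × √(2/n). At n = 18, ρ = 0.5: 1.000 × 0.333 = 0.333, 95% half-width 1.96 × 0.333 = 0.65 SD. At n = 27, ρ = 0.8: 0.632 × 0.272 = 0.172, half-width 0.34 SD.

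**The case against.** Four points can be made for the plan.

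First, a reader might infer that the plan never examines retention. That is wrong. With session 30 and week 12 as the two planned visits in the window, the group by post-TCT day interaction in Section 4.4 is the retention contrast. This stands. The fault is that it is optional, undirected, and absent from Table 1 and the Aim 2 paragraph.

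Second, a shrinking arm difference does not prove that memantine keeps a smaller share of its gain. As an assumed example, placebo going 0.4 → 0.2 and memantine 1.3 → 0.75 takes the difference from 0.9 to 0.55, yet memantine keeps 58% against 50%. This also stands: retention can be read in absolute or proportional terms, and the plan should say which it means. Scenario B shows that the rule can pass when memantine does worse on both.

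Third, a week-12 arm difference in gains from baseline is a sound measure of lasting benefit, and the plan states it openly. Agreed; the complaint is about what it is called and what is concluded from it.

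Fourth, a reader might infer that the Go rule counts the same lead twice and is inflated. The documents do not support this. Go needs one of items 2 to 4 and is not a tally. A large lead at session 30 usually shows there too: with a true D30 of 1.0, the observed d at session 30 exceeds 0.5 in 93% of trials at 18 per arm and 96.5% at 27.

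**Conclusion.** The point holds as one of labelling and inference. Item 4 and the Aim 2 paragraph can be satisfied while memantine's advantage is shrinking, and Section 4.4 can be satisfied by an arm main effect or by an interaction in the wrong direction. The identity D12 = D30 + R needs no assumption. The percentages rest on assumed gains, unit SDs and correlations of 0.5 to 0.8, and show only that the pass rate at a given D12 is the same whatever happened after session 30.

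The documents do not support going further and calling the week-12 comparison invalid or the Go decision materially distorted. The harm is a durability conclusion that the contrast cannot carry. One limit remains under any rule: participants may choose to stay on their assigned drug up to the follow-up visit, so neither D12 nor R isolates retention of training gains from continued drug exposure.

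**What to change.** In Table 1 item 4, the Aim 2 analysis paragraph and Section 4.4:

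1. Keep the week-12 arm difference with d above 0.5 as the Go item, and name it 'benefit sustained at 12 weeks'.
2. Estimate the memantine minus placebo difference in change from session 30 to week 12 from the longitudinal mixed model. Report it with its 95% confidence interval for PANSS total, MCCB composite and WHODAS, coded so that positive means improvement on each, and state that retention is measured as absolute change.
3. Base any statement that gains are more durable, in the sense of better retained, on that contrast with the direction favouring memantine stated. Do not base it on the arm main effect or an undirected interaction.

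Do not make a non-negative point estimate of this contrast a condition for Go. With a fully maintained true lead of 0.6 SD at 27 per arm, that would cut the pass rate from 64% to 37–40%, because the sign of the estimate is close to a coin toss when retention is equal.

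The visits and the model are already planned, so the cost is wording and one reported contrast. The downside is that a claim of better retention becomes harder to earn, given half-widths of about 0.34 to 0.65 SD. The Go decision is essentially unchanged.
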